1.3 Device Name

For purposes of this study, "investigational device" or "test device" refers to the REVIAN System (herein after referred to as "REVIAN"). A non-active version of the device will serve as a SHAM comparator (herein after referred to SHAM).

1.4 Brief Description of the Device

The REVIAN is a soft dome-shaped Cap that contains integrated electronics and battery technology to control delivery of modulated light therapy (MLTTM) for a daily 10-minute treatment to treat AGA and promote hair growth in men and women. The Cap contains a flexible printed circuit board (FPCB), LEDs, electronic control circuit board (PCB), lithium-polymer battery, elastic fabric and foam fitting pieces. The cap is controlled and operated by a mobile app.

REVIAN[®] Trial

2.0 PROTOCOL

2.1 Study Purpose and Objectives

The primary objective of this study is to collect data on the safety and effectiveness of REVIAN in male and female participants with AGA through 26-weeks of treatment.

2.2 Study Design Overview

This study is designed as a prospective, randomized, controlled, double-blind, four-arm study. Up to 4 clinical sites will enroll up to 200 participants over an approximate 7-month duration. Eligible participants with AGA meeting inclusion and exclusion criteria will be enrolled and randomized to one of four study arms.

```
      Study Arm 1: Active REVIAN 101 (_____ mW/cm^2 of 625 nm and 660 nm)

      Study Arm 2: Active REVIAN 102 (_____ mW/cm^2 of 425 nm)

      Study Arm 3: Active REVIAN 103 (____ mW/cm^2 of 425 nm + ____ mW/cm2 of 625 nm and 660 nm)

      Study Arm 4: Non-Active REVIAN (SHAM) Cap 100
```

The outcome measures in this study will include the following:

- Quantitative Scalp Hair Growth (Macrophotography of 1-cm² area of interest)
- Subjective Scalp Hair Growth (SSHG) score
- Physician's Global Assessment (PGA) score
- Hair Specific Skindex-29 Quality of Life Score Questionnaire

All participants will be asked to complete self-administering scalp hair growth and life quality questionnaires at each follow-up visit. Investigators will be required to complete global assessments of scalp hair growth for each enrolled participant at each follow-up visit.

Macrophotography evaluations will be performed at baseline, 8-, 16-, and 26 weeks for all participants. Global photographs of superior and vertex scalp will be taken by the PI to be assessed by a blinded reviewer once all photos have been captured for each participant per visit.

2.3 Study Scope and Participating Institutions

Participating Institutions

This study will include a maximum of 4 sites. A list of participating institutions will be provided to regulatory authorities as required.

Participant Population

Detailed enrollment criteria are provided in *Section 2.6 Participant Eligibility Criteria* of the protocol. In general, the study population will consist of adult men and women between 18 and 65 years of age with diagnosis of Androgenic Alopecia, consistent with males who have Norwood Hamilton Classification IIa to V patterns of hair loss and females who have Ludwig-Savin Scale I-1 to I-4, II -1, II-2 or frontal, both with Fitzpatrick Skin Types I – IV.

2.4 Study Endpoints

2.4.1 Primary Efficacy Endpoint:

The primary efficacy endpoint of this study is mean change in hair count from baseline to 16 weeks following the initial application at baseline.

2.4.2 Secondary Efficacy Endpoints:

Secondary efficacy endpoints will be determined using the following outcome measurement tools to evaluate changes at each follow up visit compared to baseline:

- 1. *Change from Baseline Hair Count*: Like the primary endpoint, change from baseline hair count, will also be assessed at 8 and 26 weeks.
- 2. Rate of Change in Hair Growth: The rate of change in hair growth at 8, 16, and 26 weeks will be calculated as a ratio of change from baseline to baseline.
- 3. Independent Physician's Global Assessment (iPGA): An independent reviewer will assess over hair growth over baseline from photographs, using PGA scores at weeks 8, 16 and 26. The PGA score hair growth as: -3=greatly decreased, -2=moderately decreased, -1=slightly decreased, 0=no change, 1=slightly increased, 2=moderately increased and 3=greatly increased
- 4. *Site Physician's Global Assessment (sPGA)*: The site investigator will assess over hair growth using the PGA scores at weeks 8, 16, and 26.

In addition, the percentage of participants who achieve success as defined by a PGA ≥ 2 will be summarized by treatment and by weeks.

- 5. *Subjective Scalp Hair Growth Score (SSHG): SSHG* will be administered beginning at 8 weeks and then at 16 and 26 weeks.
- 6. *Hair Specific Skindex-29 Quality of Life Score Questionnaire (HSSQOL)*: The hair specific Skindex-29 QOL questionnaire will be administered at baseline, 8, 16, and 26 weeks.
- 7. Overall Treatment Success (OTS): Overall treatment success will be defined as the number of participants who achieve ≥50% reduction in overall QOL scores, plus reported SSHG ≥2 on every question.

2.4.3 Primary Safety Endpoint(s):

At each follow-up visit, participants will be interviewed to determine if any adverse events (AEs) were experienced since the previous follow-up visit. If deemed necessary, a physical assessment may be performed for any participant experiencing a serious adverse event or as required by the Principal Investigator. The primary safety outcomes will be determined by evaluating by the type, frequency, severity, and relatedness of adverse events through the 26-week period for all participants.

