3.4.3 Randomization of Treatment Device

All participants will be randomized to one of four study arms. The randomization will be a block design, stratified across the sites and maintained by the local Study Sponsor. Each site will be blinded to the randomization code and will only receive a pre-assigned code to use for each participant at time of enrollment. The code will be pre-assigned to one of the four caps below:

Study Arm 1: Active REVIAN Cap 101Study Arm 2: Active REVIAN Cap 102Study Arm 3: Active REVIAN Cap 103Study Arm 4: Non-Active REVIAN (SHAM) Cap 100

3.4.4 Week 1 Phone Call – (7±3 Days), Visit 3

- Concomitant medication usage
- Adverse Events
- Compliance Follow-up

3.4.5 Week 8 Follow-Up Visit – (56±5 Days), Visit 4

- Subjective Scalp Hair Growth (SSHG) Score
- Physician's Global Assessment (PGA) Score
- Hair Specific Skindex-29 Quality of Life Questionnaire
- Global Photography Image of Two Views (superior and vertex scalp)
- Shave and Tattoo Scalp
- Hair Count Macrophotography (1cm² Area)
- Concomitant medication usage
- Adverse Events
- Compliance Follow-up

3.4.6 Week 16 Follow-Up Visit – (112±10 Days), Visit 5

- Subjective Scalp Hair Growth (SSHG) Score
- Physician's Global Assessment (PGA) Score
- Hair Specific Skindex-29 Quality of Life Score Questionnaire
- Global Photography Image of Two Views (superior and vertex scalp)
- Shave and Tattoo Scalp
- Hair Count Macrophotography (1cm² Area)
- Concomitant medication usage
- Adverse Events
- Compliance Follow up

3.4.7 Week 26 Follow-Up Visit – (182±10 Days), Visit 6

- Physical Exam (including vital signs)
- Subjective Scalp Hair Growth (SSHG) Score:
- Physician's Global Assessment (PGA) Score:
- Hair Specific Skindex-29 Quality of Life Score Questionnaire
- Global Photography Image of Two Views (superior and vertex scalp)
- Shave and Tattoo Scalp
- Hair Count Macrophotography (1cm² Area)
- Concomitant medication usage
- Adverse Events
- Compliance Follow up
- Exit/Termination Form

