4.2 Anticipated Adverse Events

The following AEs may be associated with the REVIAN device:

- Mechanical or electrical failure of the device or components
- Materials of Cap that may cause irritation or tissue reaction
- Allergies to Materials of Cap
- Failure to improve symptoms and/or function
- Hyperpigmentation of the treatment area

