APPENDIX B: HAIR SPECIFIC SKINDEX-29 QUALITY OF LIFE QUESTIONNAIRE

Scoring:

Sx: Symptom (7-35), Em: Emotion (10-50), Fx: Function (12-60) Total Scoring = (29-145)

APPENDIX C: Physician's Global Assessment (PGA) Scoring and Subjective Scalp Hair Growth (SSHG) Evaluations

A Canfield stereotactic positioning device will be used for obtaining global photographs where the participant's chin and forehead are fixed, and on which a given camera and flash device are mounted to standardize the view, magnification and lighting at consecutive study visits. Participants will be asked to keep the same hair style and colour and the coordinators attempt to duplicate baseline hair parting and combing in subsequent follow-up visits. Two standard views (superior and vertex) will be taken at baseline, 8-, 16, and 26-weeks (Figure 5). The digital images will be graded. Paired baseline and post-treatment photographs will be evaluated by each site study doctor (at the Week 8, 16 & 26 follow up visits) in order to provide a physician global assessment (*sPGA*) score.

In addition, the photographs will then be independently reviewed by two blinded evaluators, to evaluate the independent physician's global assessment (iPGA)

The PGA score used is the standardized 7-point rating scale (-3 = greatly decreased, -2 = moderately decreased, -1 = slightly decreased, 0 = no change, +1 = slightly increased, +2 = moderately increased, +3 = greatly increased increased).

Figure 5. Global Photography, demonstrating fixation of the participant on a brow and chin rest with the camera mounted on a rotating arm.

Participants will be asked to assess subjective scalp hair growth (SSHG). They will be provided with the following questionnaire at each follow up visit (8, 16 and 26 weeks after baseline).

Subjective Scalp Hair Growth (SSHG)

1. Since the start of the study, I can see my bald spot getting smaller

Strongly Agree	Agree	No opinion either way	Disagree	Strongly Disagree
1	2	3	4	5

2. Because of the treatment I have received since the start of the study, the appearance of my hair is:

A lot better	Somewhat better	A little better	Same	A little worse	Somewhat worse	A lot worse
1	2	3	4	5	6	7

3. Ever since the start of the study, how would you describe the growth of your hair?

Greatly increased	Moderately increased	Slightly increased	No change	Slightly decreased	Moderately decreased	Greatly decreased
1	2	3	4	5	6	7

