8. GENERAL CONSIDERATIONS FOR DATA ANALYSES

The purpose of the study is to collect data on the safety and effectiveness of *REVIAN* in participants with AGA. In general, for continuous variables, the sample size, mean, standard deviation, minimum and maximum will be presented. For categorical variables, the number and percentage in each category will be presented. All statistical analyses will be performed using SAS version 9.4 for PC. Unless otherwise specified, statistical significance will be determined using p ≤ 0.05 .

All outcomes will be provided in listings by participant and treatment group. In addition, some endpoints will be summarized in tables by treatment group.

Primary Efficacy Endpoint: The primary efficacy endpoint of this study is the change in hair count from baseline to 16-weeks following the initial application (CFB HC16).

Primary Safety Endpoint: The primary safety outcome will be determined by evaluating by the type, frequency, severity, and relatedness of adverse events through the 16-week period for all participants.

Secondary Efficacy Endpoints:

Change from Baseline Hair Count: Like the primary endpoint, change from baseline hair count, will also be assessed at 8 (CFB_HC08) and 26 (CFB_HC26) weeks.

Rate of Change in Hair Growth: The rate of change in hair growth at 8, 16, and 26 weeks will be calculated as a ratio of change from baseline to baseline.

Independent Physician's Global Assessment (iPGA): Two independent reviewers will assess overall hair growth from photographs, using PGA scores at weeks 8, 16 and 26. The PGA score hair growth as: -3=greatly decreased, -2=moderately decreased, -1=slightly decreased, 0=no change, 1=slightly increased, 2=moderately increased and 3=greatly increased. In the event the two independent reviewers do not agree, a third assessment will be made by the PI. The PI's score will superceed the two other independent reviewers' score.

Site Physician's Global Assessment (sPGA): The site investigator will assess overall hair growth using the PGA scores at weeks 8, 16 and 26.

Subjective Scalp Hair Growth Score (SHG): Beginning at Week 8, participants will complete a subjective hair growth questionnaire. The participants choose the answer that best fits the following statements:

- 1) Since the start of the study, I can see my bald spot getting smaller. (1="strongly agree" to 5="strongly disagree")

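### At weeks 8 and 16 no passage asks the site doctor to check for and record scalp hyperpigmentation, an anticipated adverse event

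*Combined protocol and SAP*

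**What the plan says.** Protocol 2.4.3 sets out how adverse events are found after baseline: "At each follow-up visit, participants will be interviewed to determine if any adverse events (AEs) were experienced since the previous follow-up visit". The next sentence adds a discretionary step: "If deemed necessary, a physical assessment may be performed for any participant experiencing a serious adverse event or as required by the Principal Investigator".

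Protocol 4.2 lists "Hyperpigmentation of the treatment area" among the events that may be associated with the device.

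After baseline, the item "Physical Exam (including vital signs)" appears only at week 26 (protocol 3.4.7 and the Study Assessment Table in 3.4.8). The week 8 and week 16 visits (3.4.5 and 3.4.6) do include "Shave and Tattoo Scalp", "Global Photography Image of Two Views (superior and vertex scalp)" and an adverse event item. Appendix C adds, for weeks 8, 16 and 26: "Paired baseline and post-treatment photographs will be evaluated by each site study doctor". The score that results is a seven-point rating of hair growth.

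SAP section 8 states: "The primary safety outcome will be determined by evaluating by the type, frequency, severity, and relatedness of adverse events through the 16-week period". Protocol 2.4.3 instead runs the primary safety endpoint to 26 weeks.

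**The concern.** Pigment change need not cause symptoms, so a participant may have nothing to report when asked about adverse events. It is also a sign that a clinician can look for, and the clinician already has the comparison to hand at weeks 8 and 16. The plan does not connect the two: the photograph comparison yields a hair-growth score, and adverse event recording starts from the interview.

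Two things are at stake. A case may never be recorded. Or it may first be noted at the week 26 examination, after a 16-week window has closed, with no reliable onset date, although protocol 4.1 requires one. Two of the three active caps use 425 nm light, which protocol 1.2 presents as new relative to existing red-light devices. The narrative in protocol 7.1 discusses cap materials and does not mention pigmentation. This trial is therefore where the frequency of the event would be learned.

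**Working it through.** The plan states no figure on this point, so the main check sets the passages side by side.

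1. *Routine detection at weeks 8 and 16.* Interview (2.4.3). No other routine step is named.
2. *Discretionary detection.* A physical assessment after a serious event or when the investigator requires it (2.4.3). Symptomless pigment change would not meet the first condition, and nothing directs the investigator to use the second for it.
3. *Scheduled examination.* Baseline and week 26 only (3.4.2, 3.4.7, 3.4.8). Week 26 is day 182 ± 10 and week 16 is day 112 ± 10. The earliest in-window examination is day 172, and the latest in-window week 16 visit is day 122. The examination therefore falls at least 172 − 122 = 50 days after the end of the week 16 window.
4. *Opportunity to see the scalp.* The investigator takes superior and vertex photographs (2.2), and the site doctor compares them with baseline (Appendix C). The rating scale has no skin item.
5. *Questionnaires.* The Skindex-29 in Appendix B asks about pain, burning or stinging, itch, irritation, sensitivity and bleeding. No item asks about colour.
6. *Need for a baseline.* Protocol 4.1 counts a pre-existing sign as an adverse event only if it worsens. The photographs supply that comparison; an interview does not.
7. *Primary safety window.* 16 weeks in the protocol summary, 2.7, 5.1 and SAP 8; 26 weeks in 2.4.3.

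The following calculation is an illustration only. Let n = 50 per arm (protocol 5.2), p be the true incidence and s the share of cases detected. Both p and s are assumed. Expected recorded cases = n × p × s. Chance of recording at least one = 1 − (1 − p × s)^50.

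| Assumed p | s = 1 | s = 0.5 | s = 0.25 |
|---|---|---|---|
| 2% | 1.0 cases; 64% | 0.5; 40% | 0.25; 22% |
| 5% | 2.5; 92% | 1.25; 72% | 0.63; 47% |
| 10% | 5.0; 99.5% | 2.5; 92% | 1.25; 72% |

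For example, at p = 5% and s = 0.5: 1 − (1 − 0.025)^50 = 72%. The column s = 1 is an upper bound, because a photograph review would also miss some cases.

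On the comparison between arms: if s is the same in every arm and there are no false positives, the expected difference is s × (p_active − p_sham), which shrinks in proportion to s. The expected ratio p_active / p_sham does not change.

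**The case against.** The case against starts with what the investigator already does. Investigators must be qualified in dermatological conditions of the scalp (protocol 3.4.2). They photograph the scalp and compare it with baseline, and at the same visits they record adverse events, which protocol 4.1 says should be diagnosed from signs as well as symptoms. One who noticed new pigmentation would be expected to record it. On this view only a prompt is missing. That is largely right, and it sets the limits of the point. But confirming a diagnosis by signs applies once an event has been raised; it does not require anyone to look.

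A reader might infer several stronger things that the documents do not support:

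- *Interview is the only route.* It is the only routine one named; 2.4.3 also allows an assessment that the investigator requires.
- *Participants cannot see the change.* No passage says so. Eligible participants have thinning or bald areas, so treated skin may be exposed.
- *The event will be under-counted, biasing the trial towards no difference.* This is a risk, not something shown. Safety is summarised descriptively without a between-arm test, and equal under-detection leaves the expected ratio unchanged.
- *Irritation is equally exposed.* It is felt, and the Skindex-29 already asks about it.

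Two further limits stand. The CRFs and the Macrophotography Technique Manual are not in the documents, so a skin item may exist there. And hair cover that limits what a participant sees also limits what a photograph shows.

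**Conclusion.** The point holds as a gap in ascertainment, confined to hyperpigmentation. At weeks 8 and 16 an anticipated adverse event is left to participant report or chance notice, and the first scheduled examination comes after the 16-week window. Cases without symptoms may be missed or dated too late.

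Its size cannot be estimated. The table shows only how the result would move under assumed values. At 10% incidence, detecting half the cases still leaves a 92% chance of recording at least one in an arm; at 2% the same loss takes that chance from 64% to 40%. If incidence were the same in all three active arms, pooling them would make a complete miss less likely still: at 10% incidence and 30% detection, the chance of no recorded case in 150 is 0.97^150, about 1%.

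The timing argument depends on the 16-week window. Under the 26-week window in 2.4.3, the week 26 examination falls at the end of the window and could catch change still present then. The absence of a prompt at weeks 8 and 16 remains under either window. This is an inexpensive improvement worth making, not a defect that undermines the safety analysis.

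**What to change.** At Visits 4, 5 and 6, add one CRF item for the blinded site doctor to complete when comparing the global photographs with baseline for sPGA: new or worse pigment change of the treated scalp, yes or no. Judge it outside the shaved and tattooed 1 cm² field, so that ink or shaving effects are not read as device effects. Record a yes as an adverse event, and tabulate by arm at 16 and 26 weeks. If the CRF already carries such an item, state it in the protocol and SAP. Irritation need not be added.

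Reconcile the primary safety window between protocol 2.4.3 (26 weeks) and the summary, 2.7, 5.1 and SAP 8 (16 weeks).

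The cost is one item at three existing visits, with no new visit, procedure or staff. The baseline photographs already serve as the comparator. The downside is that more mild skin events will be recorded.

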2.5 Study Population and Source of Participants

All participants with diagnosis of androgenic alopecia may be eligible for study participation. Potential study candidates will be approached for consent prior to any data collection. A screening and enrollment log will be provided to study sites to maintain a record of all screened participants.

Participants will be identified and recruited by Clinical Investigators and/or their designated research staff at facilities affiliated with a maximum of 4 investigative sites. Clinical Investigators selected to participate in the study should be able to enroll at least 10 participants per month with a maximum of 100 participants enrolled at a single site.

For the purposes of enrollment, only those participants who meet all eligibility criteria, sign an IRB/HREC approved consent form and begin treatment with REVIAN/SHAM will be considered enrolled in the study. Participants who consent to participate but withdraw prior to the first treatment with REVIAN/SHAM will be considered a screening failure and the reasons for screening failure will be documented on the site screening log. All treated participants will be evaluated for the primary endpoints at 16-weeks.

Any participant consented, whether treated or not, will be assigned a screening number. The reason for failure to treat will be recorded in his/her study records and the site screening log.

2.6 Participant Eligibility Criteria

Inclusion Criteria:

Candidates for this study must meet ALL of the following criteria:

- 1. Male and Female participants between 18 and 65 years of age
- 2. Must be able to read and speak English.
- 3. Participants who are able to give voluntary, written informed consent to participate in this clinical investigation and from whom consent has been obtained.
- 4. Participants, who, in the opinion of the Clinical Investigator, are able to understand this clinical investigation, cooperate with the investigational procedures and are willing to return for all the required follow-up visits.
- 5. Participant must be able to visit clinic site at 8-, 16- and 26-weeks study visits and be available by phone at 4 weeks.
- 6. Participant must have the ability to communicate effectively with study personnel in person or over the phone.
- 7. Participant must have diagnosis of Androgenic Alopecia (pattern hair loss).
- 8. Participant must have active hair loss consistent with Grades IIa to V, based on Norwood-Hamilton Scale or Ludwig-Savin Scale I-1 to I-4, II -1, II-2 or frontal and Grades I - IV using Fitzpatrick Skin Type Scale.
- 9. Participant's hair must be at least 1 inch in length. The hair style and length shall be the same for each follow-up visit. Participants will be instructed to not have their hair cut/styled within 5 days prior to a follow-up visit.
- 10. Participant is willing to have a dot tattoo placed on or around the target area of the scalp.
- 11. Participant is willing to undergo all study procedures including consent for global photographs of hair loss/growth and a 1 mm tattoo to mark the macrophotography site along the indicated transition area of the scalp between the hairline and the balding/thinning vertex area.
- 12. Participant is willing to avoid the use of wigs, hairpieces, and/or hair extensions during the study period.
- 13. Hair Specific Skindex-29 Quality of Life total overall score of \geq 45.
- 14. Participant is willing to maintain their natural hair colour or including the use of coloring throughout the study period.
- 15. Participant agrees to refrain from using all other hair growth products or treatments (oral or topical medication including over the counter herbal medications, or Dutasteride) during the study period.
- 16. Participant has the ability to utilize a Bluetooth device and application on a smart device connected to Wi-Fi.

Exclusion Criteria:

Candidates will be excluded from the study if ANY of the following apply:

- 1. Female participants of childbearing potential who are not on some form of birth control and do not have a confirmed negative pregnancy test at baseline
- 2. Use of Propecia or any other hair growth supplements within 12 months prior to enrollment.
- 3. Use of Rogaine or Minoxidil based products within 6 months prior to enrollment.
- 4. Participants have a previous hair transplant, cell treatment, micro needling, tattooing, or any other treatment to the scalp.
- 5. Participant is suffering from an active autoimmune disease such as lupus erythematosus (systemic and cutaneous) or alopecia areata.
- 6. Photosensitivity to visible light operating within 400 850 nm or taking medication that

increases photosensitivity.

- 7. Currently suffering from a dermatological condition in the treatment area or has a significant scar in the hair treatment area that, in the opinion of the investigator, will make hair growth difficult (such as a systemic burn, malignancy, etc.)
- 8. Participant has a sensitivity or allergy to tattoo ink.
- 9. Using any medication deemed to inhibit hair growth as determined by the physician investigator.
- 10. Employed by the sponsor, clinic site, or entity associated with the conduct of the study.
- 11. Has had radiation or chemotherapy in the last 12 months.
- 12. Have any condition or situation which, in the Investigator's opinion, puts the participant at significant risk, could confound the study results, or may interfere significantly with the participant's participation in the study.
- 13. Known prior inability to complete required study visits during treatment period;
- 14. Use of any other investigational drug, therapy, or device within the past 30 days of enrollment or concurrent participation in another research study;
- 15. Are unable to communicate or cooperate with the Investigator due to language problems, poor mental development, or impaired cerebral function;
- 16. Participants who are currently involved in any investigational drug or device trial or have been enrolled in such trials within the last 3 months.

